3.2. Rationale of Study Design

Subjects eligible for this KPL-914-C002 study will be subjects with recurrent pericarditis presenting with an acute pericarditis episode at screening.

The KPL-914-C002 study design ensures that during the RI period all subjects will receive rilonacept, a drug with evidence supporting clinical activity based on the clinical data with rilonacept from the Phase 2 proof-of-concept study (KPL-914-C001). During the RI period, pericarditis will be stabilized with symptoms controlled and background pericarditis medications (NSAIDs, colchicine, CS) will be tapered and withdrawn, while rilonacept treatment continues.

The design then allows half of the subjects to continue receiving active treatment after having achieved Clinical Response on that treatment, which maximizes subject exposure to a potentially beneficial therapy. The temporary withdrawal of rilonacept (by switching to placebo) in the half of the subjects who were randomly assigned to placebo is expected to result in an accelerated time to pericarditis recurrence and a higher recurrence rate compared to those who continue on active treatment, a finding that demonstrates that the underlying pericarditis etiology is still ongoing and will provide further support for the anticipated observation of the clinical effect of rilonacept during the RI period of the study. The period of exposure to an ineffective treatment is minimized in this design, as subjects will be removed from blinded treatment when the condition returns to a specified severity (i.e., for having met the criteria of pericarditis pain ≥ 4 on the 11-point NRS and CRP level ≥ 1 mg/dL) without unblinding them to prior treatment assignment, thus protecting the primary efficacy endpoint of the study. All subjects who meet the pain and CRP criteria described above will be treated with open-label bailout rilonacept using a loading dose, followed by once-weekly SC injections. In addition, sequential ORT such as NSAIDs and/or colchicine will be allowed upon recurrence at the Investigator's discretion based on the subject's clinical status, as outlined in Section 5.6.3 and as stipulated in the Pharmacy Manual. Subjects with pericarditis recurrence not meeting criteria for bailout rilonacept, can be treated with sequential ORT based on Investigator judgement and as described in protocol Section 5.6.3 and the Pharmacy Manual. If the subject requires the addition of CS treatment to control the pericarditis recurrence, the subject will be discontinued from study drug. All subjects will be followed for the duration of RW period.

In summary, the proposed RW trial with rilonacept allows all enrolled subjects an opportunity to receive the active drug during the acute episode of pericarditis yet provides pivotal-quality data on the efficacy of rilonacept in this enriched cohort by subsequently randomly assigning subjects to placebo versus active treatment after they achieve a predefined clinical response. Subjects with pericarditis recurrences after randomization will receive bailout rilonacept treatment and/or sequential ORT according to the protocol. This approach minimizes the exposure to placebo, which is important for a study that requires active disease upon enrollment and includes a pediatric population. The available regulatory guidance supports the use of an RW study design in the setting of recurrent pericarditis as a

means of establishing the long-term effectiveness of rilonacept, an approved product for the treatment of another rare autoinflammatory condition (CAPS).

3.3. Justification for Dose Selection

[REDACTED]
[REDACTED] i.e., 320 mg SC loading dose (4.4 mg/kg in subjects ≥ 12 and < 18 years old), followed by once-weekly SC doses at 160 mg (2.2 mg/kg in subjects ≥ 12 and < 18 years old).

In the rilonacept development program in CAPS, gout, rheumatoid arthritis, and other inflammatory conditions, over 2000 subjects were exposed to rilonacept, including 1650 subjects receiving a rilonacept dose of 160 mg or higher. A total of 103 and 169 subjects were exposed to any rilonacept dose for at least 1 year or 6 months, respectively. Most of the real-life experience with rilonacept comes from the CAPS population treated at this marketed dose. As of March 2018, approximately 365 CAPS patients have been exposed to rilonacept in the post-marketing setting since 2008. The safety data accumulated so far support the benefit/risk ratio for the rilonacept dose intended to be evaluated in subjects with recurrent pericarditis.

Based on the clinical data with rilonacept from the Phase 2 proof of concept study (KPL-914-C001), it is expected that rilonacept doses [REDACTED] (320 mg followed by 160 mg SC once weekly and corresponding pediatric doses), and evaluated in the KPL-914-C001 study, will consistently provide adequate suppression of clinical inflammatory response, including CRP levels, in patients with recurrent pericarditis.

Subjects who meet the protocol criteria for **bailout rilonacept** upon pericarditis recurrence in the RW period of the study (Sections 3.1 and 6.2.3), irrespective of treatment assignment at randomization, will receive open-label rilonacept (loading dose of 320 mg SC followed by once-weekly SC injections of 160 mg, or the corresponding pediatric doses). [REDACTED]

The rationale for bailout rilonacept treatment upon pericarditis recurrence for subjects who were randomly assigned to placebo is that rilonacept had controlled their disease activity during the RI period; therefore, re-initiation of rilonacept is justified to regain control of pericarditis signs and symptoms upon recurrence. Subjects who were randomly assigned to rilonacept and qualify for bailout rilonacept upon pericarditis recurrence in the RW period were initial responders to rilonacept treatment during the RI period; thus it could be assumed that the loss of response during the RW period could be due to development of resistance to rilonacept due to different mechanisms, e.g., higher IL-1 levels or a change in rilonacept pharmacokinetics (PK)/ pharmacodynamics. Therefore, re-administration of a loading dose of rilonacept may help to restore Clinical Response.

4. SELECTION OF STUDY POPULATION

Up to approximately 100 subjects with recurrent pericarditis will be enrolled, which will allow accrual of at least 22 adjudicated pericarditis recurrence events in randomized subjects at approximately 50 sites globally. Subjects will be assigned to study drug only if they meet all of the inclusion criteria and none of the exclusion criteria.

Deviations from the inclusion and exclusion criteria are not allowed because they can potentially jeopardize the scientific integrity of the study, regulatory acceptability, or subject safety. Therefore, adherence to the criteria as specified in the protocol is essential.

Subjects eligible for the study are subjects with recurrent pericarditis who do not have pericarditis secondary to prohibited conditions. The study population includes both adult subjects ≥ 18 years old and pediatric subjects ≥ 12 and < 18 years old with a history of at least 2 pericarditis episodes (including the first episode and 1 recurrence) prior to screening. Enrollment of pediatric subjects will be limited to up to 20% of the study population. To be eligible for the study, subjects must present with at least a third pericarditis episode, defined as at least 1 day with pericarditis pain measurement ≥ 4 on the 11-point NRS and CRP level ≥ 1 mg/dL within 7 days prior to the first study drug administration.

4.1. Inclusion Criteria

Each subject must meet all of the following criteria to be enrolled in this study:

1. Is capable of understanding the written informed consent form (ICF) or assent form (for pediatric subjects ≥ 12 and < 18 years old), has provided signed and witnessed written informed consent or assent (as applicable), and agrees to comply with protocol requirements.
2. Is male or female 12 years of age or older with body weight of at least 23.6 kg (52 Lbs).
3. Has a diagnosis of recurrent pericarditis.
4. At least 1 of the pericarditis episodes experienced prior to screening has met at least 2 of the following 4 criteria, in the opinion of the Investigator and based on the documented available data, according to the 2015 ESC Guidelines for the Diagnosis and Management of Pericardial Diseases (Adler et al 2015):
 - a. Pericarditic chest pain
 - b. Pericardial rub
 - c. New widespread ST-segment elevation or PR-segment depression according to ECG findings
 - d. Pericardial effusion (new or worsening)
5. Presents with at least the third episode of pericarditis during screening (i.e., at least the second pericarditis recurrence following the first pericarditis episode), and within 7 days* prior to and including RI baseline (first administration of study drug) has:
 - a. At least 1 day with pericarditis pain ≥ 4 on the 11-point NRS, **AND**

- b. CRP level ≥ 1.0 mg/dL (for details of CRP collection see Section 6.1.1)
*Pericarditis pain ≥ 4 and CRP ≥ 1 mg/dL are not required to be present on the same day.
6. Has received NSAIDs and/or colchicine and/or CS (in any combination), if used, at stable dose levels (or at least not increased) for at least 3 days prior to and including RI baseline (first administration of study drug), and changes in medications made within this time period (e.g., 1-time use of NSAIDs) are not anticipated, in the opinion of the Investigator, to significantly alter assessments of baseline disease activity.
7. If using NSAIDs and/or colchicine and/or CS at the time of RI baseline (first administration of study drug), is willing and able, in the opinion of the Investigator, to taper and discontinue those medications within the 9-week weaning time in the RI period of the study while continuing rilonacept treatment.
8. Female subjects must be:
 - a. Postmenopausal, defined as at least 12 months after the cessation of menses (without an alternative medical cause) OR
 - b. Incapable of pregnancy OR
 - c. Permanently sterile following documented hysterectomy, bilateral salpingectomy, bilateral oophorectomy, or bilateral tubal ligation or having a male partner with vasectomy as affirmed by the subject OR
 - d. If of childbearing potential, must agree to use a highly effective method of contraception during the study and for 3 months after the last study drug administration (e.g., hormonal contraceptives associated with inhibition of ovulation, intrauterine device [IUD], intrauterine hormone-releasing system [IUS], or sexual abstinence)
9. If male and sexually active, must have documented vasectomy or must practice birth control and not donate sperm during the study and for 3 months after the last study drug administration.
10. Must be up-to-date with all immunizations, in agreement with current local immunization guidelines for immunosuppressed subjects, before RI baseline (first administration of study drug).
11. Is able to adequately maintain a daily subject diary according to protocol.
12. Must be able to adhere to the study visit schedule and understand and comply with the other protocol requirements.
13. Agrees to refrain from making any new, major lifestyle changes that may affect pericarditis symptoms (e.g., changing exercise pattern) from the time of the ICF is signed through the end of the double-blind RW period.

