Although malignancies have been reported in some subjects treated with rilonacept during clinical trials, the effect of rilonacept on the development of cancer is not known. Treatment with immunosuppressants, including rilonacept, may result in an increase in the risk of malignancies.

Fetal Defects

There are no adequate and well-controlled studies of rilonacept in pregnant women. Based on animal data, rilonacept may cause fetal harm. An embryo-fetal developmental toxicity study was performed in cynomolgus monkeys treated with 0, 5, 15, or 30 mg/kg given twice a week (highest dose is approximately 3.7-fold higher than the human dose of 160 mg based on body surface area). The fetus of the only monkey with exposure to rilonacept during the later period of gestation showed multiple fusion and absence of the ribs and thoracic vertebral bodies and arches. Exposure to rilonacept during this time period was below that expected clinically. Likewise, in the cynomolgus monkey, all doses of rilonacept reduced serum levels of estradiol up to 64% compared to controls and increased the incidence of lumbar ribs compared to both control animals and historical control incidences. In perinatal and postnatal developmental toxicology studies in the mouse model using a murine analog of rilonacept (0, 20, 100, or 200 mg/kg), there was a 3-fold increase in the number of stillbirths in dams treated with 200 mg/kg 3 times per week (the highest dose is approximately 6-fold higher than the 160 mg maintenance dose based on body surface area).

Nonteratogenic effects: A peri- and postnatal reproductive toxicology study was performed in which mice were administered a murine analog of rilonacept at doses of 20, 100, and 200 mg/kg SC 3 times per week (the highest dose is approximately 6-fold higher than the 160 mg maintenance dose based on body surface area). Results indicated an increased incidence in unscheduled deaths of the F1 offspring during maturation at all doses tested.

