6.3. Safety Assessments

Safety assessments to be performed at study visits are summarized in Section 13.1 and include: assessment of AEs (Section 6.4), physical examinations (full and abbreviated) including vital signs measurements, chest x-ray, TB screening, and clinical laboratory tests (serology, hematology, chemistry, urinalysis) (Section 6.6). A pregnancy test (Section 6.6.6) will be conducted at screening and as needed during the study and must be performed 6 weeks after the last study drug administration.

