6.6.6. Pregnancy Test

For women of child-bearing potential, a urine pregnancy test using a licensed test (dipstick) should be performed prior to receiving the first administration of study drug and as needed during the study. When needed, serum pregnancy test should be performed. The purpose of pregnancy test is to prevent embryo/fetal exposure to study drug. Subjects with positive or indeterminate pregnancy test during the screening are not eligible for the study.

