IWRS Subject Status Update	X	X								X
IWRS Weight Input (pediatric only)		X								X
IWRS Drug Dispensing		X		X				X		X
In Clinic Study Drug Administration ^o		X ⁿ						X		X
Outpatient Study Drug Administration ^o					WEEKLY					
Study Drug Compliance Review		X			X	X	X	X	X	X
Clinical Response Evaluation										X ^p
Adverse Event Reporting ^l	X	X		X	X	X	X	X	X	X

a The screening and enrollment visit can be combined.

b Scheduling of visits within visit windows requires cautious planning to ensure there is no interruption to subject evaluation and study drug treatment.

c Full physical examination includes at minimum evaluation of vital signs, head, eye, ear, nose, and throat as well as cardiovascular, dermatological, musculoskeletal, respiratory, GI, genitourinary, and neurological systems. The decision to perform examination of genitourinary system should be guided by clinical judgement.

d Abbreviated physical examination includes at minimum evaluation of vital signs, lung and heart sounds, including evaluation for pericardial rub.

e ECHO is required to be obtained according to the central core lab parameters and then read locally and submitted to the central core lab for separate review and analysis.

f Both a documented CRP ≥ 1.0 mg/dL AND a pericarditis pain level of ≥ 4 is required 7 days prior to and including the Run-In Baseline visit. These are not required to occur on the same day.

g Subjects missing ≥ 4 daily pain measurements during the 7 days prior to and including the Randomization Withdrawal baseline visit will be unable to proceed to randomization due to lack of data required for treatment response evaluation.

h Lipid panels are non-fasting and are to be drawn at a minimum of every 6months during the randomization withdrawal and LTE periods, or more frequently as needed, with mandated evaluations as detailed in the schedule of events.

i Applicable to 24-hour post dose PK sub-study participants only.

j For women of child bearing potential - urine pregnancy testing can be repeated as needed throughout the course of the study and serum pregnancy can be drawn as needed; urine pregnancy is required to be performed at enrollment and 6 weeks after the last dose of study drug.

k Pharmacogenomics informed consent and subsequent sampling can be performed at any time in the study however, it is preferable to have this completed at the beginning of the study.

- l Adverse event reporting begins following the subject providing informed consent.

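### Inclusion criterion 8c groups a partner's vasectomy with the woman's own sterilisation, so a fertile woman can enter outside 8d and may be read as exempt from its contraception duty and from the required pregnancy tests

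*Protocol*

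**What the plan says.** Criterion 8 (Section 4.1, Version 3.0) requires a female subject to meet one of four limbs joined by OR: postmenopausal (8a), unable to become pregnant (8b), 8c or 8d.

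- **8c:** "Permanently sterile following documented hysterectomy, bilateral salpingectomy, bilateral oophorectomy, or bilateral tubal ligation or having a male partner with vasectomy as affirmed by the subject".
- **8d:** "If of childbearing potential, must agree to use a highly effective method of contraception during the study". The duty continues for 3 months after the last dose.

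Section 4 forbids deviations from the eligibility criteria and adds that "adherence to the criteria as specified in the protocol is essential".

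Pregnancy testing is set out in three places:

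- **Section 6.3** says that a pregnancy test, with a cross-reference to Section 6.6.6, "will be conducted at screening and as needed during the study and must be performed 6 weeks after the last study drug administration". It names no group of subjects.
- **Section 6.6.6** addresses its urine test to women of childbearing potential. It places the test before the first dose and then as needed, and makes a positive or indeterminate screening result disqualifying.
- **Footnote j** in Tables 2 to 5 of Section 13.1 applies to the same group and states that "urine pregnancy is required to be performed at enrollment and 6 weeks after the last dose of study drug".

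On the purpose, Section 6.6.6 explains that the "pregnancy test is to prevent embryo/fetal exposure to study drug". Section 1.3.1 states: "Based on animal data, rilonacept may cause fetal harm".

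**The concern.** Limb 8c mixes two different things. Hysterectomy, salpingectomy, oophorectomy and tubal ligation change the woman's own ability to conceive. A partner's vasectomy does not; it is contraception that depends on one particular partner. Placed in 8c, it opens a route into the trial for a fertile woman that carries no contraception undertaking, no duration and no instruction for a change of partner.

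The effect may reach beyond eligibility. The testing rules depend on childbearing potential, and the only place that sorts women by that property is criterion 8, where the phrase appears in 8d alone. A site could therefore class the 8c woman with the surgically sterile and omit her pregnancy tests. What is at stake is undetected embryo or fetal exposure to a drug that the protocol itself flags for possible fetal harm.

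**Working it through.** This is a question of wording and logic, apart from one count.

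**1. Route through criterion 8.** The limbs are alternatives, so meeting one is enough. Take a premenopausal woman with no sterilising surgery whose partner has had a vasectomy.

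| Limb | Does she meet it? | Contraception duty |
|---|---|---|
| 8a | No | None |
| 8b | No | None |
| 8c | Yes, through the partner clause | None |
| 8d | Not needed once 8c is met | During the study and 3 months after the last dose |

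The partner clause can be read in two ways: as one form of permanent sterility, or as a separate alternative inside 8c. On both readings she enters by 8c, and the 8d undertaking need not be obtained from her.

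**2. Who must be tested.** Section 6.6.6 and footnote j both limit testing to women of childbearing potential. Section 6.3 has no such limit, but it points to Section 6.6.6, which does. The protocol gives no definition of the term. In plain meaning this woman falls within it; on the contrast that criterion 8 draws between 8d and the other limbs, she can be taken to fall outside it. The text does not settle which reading a site should use.

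**3. Number of tests that depend on this reading.** Scheduled urine pregnancy tests, all marked with footnote j:

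| Source | Visits | Tests |
|---|---|---|
| Table 2 | Screening, RI baseline | 2 |
| Table 3 | End of randomized withdrawal (EORW) | 1 |
| Table 4 | LTE Week 24, LTE 18-month assessment | 2 |
| Table 5 | Safety follow-up | 1 |

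Total with the LTE: 2 + 1 + 2 + 1 = 6. Without the LTE: 2 + 1 + 1 = 4. Section 6.1.1 lets screening and RI baseline be combined without repeating shared procedures, which lowers these to 5 and 3. Footnote j names two tests as required, at enrollment and 6 weeks after the last dose. No woman has a scheduled test between RI baseline and EORW, so that interval is not part of this gap.

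**4. How long partner status at entry must hold.** Section 3.1.4 projects dosing of up to 2 years by the end of the RW period and up to 24 months more in the LTE: 2 + 2 = 4 years at most. Nothing in 8c requires partner status to be rechecked in that time or in the months after the last dose.

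**5. Standard of proof.** Under criterion 9 a male subject's vasectomy must be documented. Under 8c the partner's vasectomy rests on the subject's own statement.

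**The case against.** The case on the other side has four parts.

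- **Plain meaning.** A woman who has not been sterilised is of childbearing potential whatever her partner's surgery. Neither Section 6.6.6 nor footnote j refers to criterion 8, so a careful site would test her. Nothing in the protocol calls her exempt.
- **8d may already cover her.** The OR between limbs is not exclusive. The list of methods in 8d, closed in Version 2.0, is given as examples in Version 3.0, so a vasectomised partner could be accepted there as a method.
- **Other safeguards apply to every woman.** Section 6.3 speaks of testing without naming a group. Exclusion 2 bars pregnancy and planned pregnancy, Section 4.3.2.1 stops dosing for either, and Sections 6.4.6.1 and 6.4.7 require prompt reporting and follow-up of any pregnancy.
- **The added risk is small while the partner stays the same,** because his vasectomy is itself contraception.

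Much of this stands, and it limits the finding to what a site may read, not what the protocol orders. It does not remove the finding. That she could also meet 8d does not oblige a site to apply it once 8c is met. Section 6.3 refers back to the section that carries the restriction. The exclusion and the stop rule need a pregnancy to be known; without the tests they rest on history and self-report. The change of partner is covered nowhere.

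**Conclusion.** The concern holds. A fertile woman with a vasectomised partner can satisfy criterion 8 without the contraception duty in 8d; that follows directly from the OR structure. That she may also be treated as outside the testing rules is a reasonable literal reading of an undefined term, not something the protocol states. On that reading, up to 6 scheduled urine tests (4 without the LTE) are open to omission, including the two that footnote j requires.

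The document does not say how many women would enter through 8c, and no headcount or pregnancy risk is estimated here. Exclusion 2 and the pregnancy stop rule still apply to her. The issue is one of subject safety and consistent conduct across about 50 sites; it has no bearing on type I error, power or the primary analysis. The change should be made, because the rule misclassifies a contraceptive method and is cheap to correct. A statistical analysis plan would not cure it, since eligibility and pregnancy testing belong in the protocol.

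**What to change.** Delete the partner clause from 8c, leaving only the woman's own surgical sterility. Add to the methods in 8d a vasectomised sole partner, affirmed by the subject, with a duty to use another highly effective method if the partner changes during the study or in the 3 months after the last dose. State in Section 6.6.6 and footnote j that every woman who enters through 8d counts as of childbearing potential.

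The cost is one clause moved, one clarifying sentence, and a few dipstick tests at visits already in the schedule.
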